9.10. Safety monitoring

9.10.1. Safety Review Team

The project's SRT includes as core members the GSK Biologicals' Central Safety Physician, the Clinical Research & Development Lead (CRDL), Epidemiologist, Clinical Regulatory Affairs representative and the Biostatistician of the project. The SRT is responsible for on-going safety monitoring of the entire project and meets on a regular basis. The SRT will inform the iSRC about any potential safety concern relevant to the study.

Before each iSRC safety evaluation in this study (see below), the SRT will review the same safety data, but in a *blinded* manner in order to keep all people involved in the conduct, cleaning and final analysis of the study blinded.

9.10.2. Internal Safety Review Committee

As the investigational vaccine will be administered for the first time to moderate and severe COPD patients, an iSRC will be appointed next to the existing project's SRT and safety holding rules have been defined (see [Table 24](#)).

[figure not shown]
The iSRC will be authorised by GSK Biologicals' VSMB and its core members will include a GSK Biologicals' Safety Physician, a CRDL and a Biostatistician who are not otherwise involved in the conduct of the project. If none of the core members listed above is a respiratory expert, such an expert will be included.

The iSRC will conduct *unblinded* reviews of all available safety data from the present study, including data on AECOPD (frequency, intensity and duration), while taking into account any other findings that could have an impact on the safety of the subjects, and will determine whether there is a safety signal that needs to be escalated to GSK Biologicals' VSMB. In the event that a safety signal is observed, GSK Biologicals' VSMB might decide to suspend, modify or continue the conduct of the study.

Administration of **vaccine Dose 1** will follow a **staggered** design, starting with vaccination of GOLD 2 subjects only. Administration of vaccine Dose 1 to GOLD 3 subjects will depend on the favourable outcome of an iSRC evaluation of safety data up to at least day 6 after vaccination from about 20 GOLD 2 subjects (*i.e.* approximately 10 subjects/ group).

In addition, starting administration of **vaccine Dose 2** will for each GOLD grade depend on the favourable outcome of an iSRC evaluation of all available safety data.

In addition to the planned iSRC evaluations, *ad hoc* safety evaluations can take place if a safety concern is identified by an investigator (*e.g.* meeting of holding rules 1a-c) or by the SRT.

Figure 2 Overview of iSRC evaluation

SE = safety evaluation

* Safety evaluation on all available safety data, before the first subject needs to be administered vaccine Dose 2. In addition to the SEs depicted above, *ad hoc* safety evaluations can take place (for instance if holding rule 1a-c is met).

9.10.3. Study holding rules

As the investigational NTHi vaccine will be administered for the first time to moderate and severe COPD patients, study holding rules have been defined (see [Table 24](#)).

- **Holding rules 1a, 1b and 1c** will be monitored by the investigators on a continuous basis for as long as vaccination is on-going in the study. Meeting any of these holding rules will trigger a hold of vaccination irrespective of the number of subjects vaccinated.
- **Holding rules 2a, 2b and 2c** will be assessed by the iSRC during the safety evaluations.

Table 24 List of holding rules

Holding Rule	Event	Number/percentage of subjects
1a	Death or any life-threatening SAE	≥ 1
1b	Any withdrawal from the study (by investigator or subject request) following a Grade 3 AE that cannot reasonably be attributed to a cause other than vaccination	≥ 1
1c	Any local or general solicited AE leading to hospitalisation, or body temperature > 40°C that cannot reasonably be attributed to a cause other than vaccination, or necrosis at the injection site, within the 7-day (days 0-6) post-vaccination period	≥ 1
2a	Any Grade 3 solicited local AE lasting 48 hours or more in the investigational group, within the 7-day (day 0-6) post-vaccination period	≥ 25% AND ≥ 2 subjects/group
2b	Any Grade 3 general solicited AE lasting 48 hours or more in the investigational group, that cannot reasonably be attributed to a cause other than vaccination, within the 7-day (day 0-6) post-vaccination period.	≥ 25% AND ≥ 2 subjects/group
2c	Any Grade 3 unsolicited AE in the investigational group, that cannot reasonably be attributed to a cause other than vaccination, within the 7-day (day 0-6) post-vaccination period or Any ≥ Grade 3 abnormality* in pre-specified haematology or biochemistry laboratory parameter in the investigational group, if it cannot reasonably be attributed to a cause other than vaccination, at day 7 post-vaccination.	≥ 25% AND ≥ 2 subjects/group

[figure not shown]
* Grading of biochemistry parameters will be based on the FDA Guidance for Industry "Toxicity Grading Scale for Healthy Adult and Adolescent Volunteers Enrolled in Preventive Vaccine Clinical Trials" (see [APPENDIX C](#)).

Risk assessment curves - probability of meeting holding rules

[Figure 3](#) illustrates for example that:

- **With 10 subjects/ group:**
 - Each holding rule 1 (a-c) has more than 90% chance of not being met for a vaccine with a true incidence rate below 1% and has more than 90% chance of being met for a vaccine with a true incidence rate above 20%.
 - Each holding rule 2 (a-c) has almost 100% chance of not being met for a vaccine with a true incidence rate below 1% and has more than 30% chance of being met for a vaccine with a true incidence rate above 20%.
- **With 20 subjects/ group:**
 - Each holding rule 1 (a-c) has more than 80% chance of not being met for a vaccine with a true incidence rate below 1% and has more than 98% chance of being met for a vaccine with a true incidence rate above 20%.
 - Each holding rule 2 (a-c) has almost 100% chance of not being met for a vaccine with a true incidence rate below 1% and has more than 55% chance of being met for a vaccine with a true incidence rate above 20%.

Figure 3 Risk assessment curves for safety holding rules 1 and 2 for treatment arms of 10 or 20 subjects (no adjustment for multiplicity)

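### Holding rule 2 with 20 subjects per group has a 37% chance of being met at a 20% true rate, not the more than 55% that the protocol states

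*Protocol*

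**What the plan says.** Table 24 in Protocol section 9.10.3 sets the trigger for rules 2a, 2b and 2c at "≥ 25% AND ≥ 2 subjects/group". The count is of vaccinees only; rule 2a, for example, covers "Any Grade 3 solicited local AE lasting 48 hours or more in the investigational group, within the 7-day (day 0-6) post-vaccination period". Rules 1a to 1c trigger on a single event.

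The text below the table gives the chance of meeting each rule, read from Figure 3, whose caption is "Risk assessment curves for safety holding rules 1 and 2 for treatment arms of 10 or 20 subjects (no adjustment for multiplicity". At a 20% true rate it states:

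- 10 subjects per group, rule 1: "has more than 90% chance of being met for a vaccine with a true incidence rate above 20" percent.
- 10 subjects per group, rule 2: "has more than 30% chance of being met for a vaccine with a true incidence rate above 20" percent.
- 20 subjects per group, rule 1: "has more than 98% chance of being met for a vaccine with a true incidence rate above 20" percent.
- 20 subjects per group, rule 2: "has more than 55% chance of being met for a vaccine with a true incidence rate above 20" percent.

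It also gives the chance that each rule is not met at a true rate below 1%: above 90% (10 subjects) and above 80% (20 subjects) for rule 1, and close to 100% for rule 2.

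**The concern.** A trigger set at 25% of subjects should be met less than half the time when the true rate is only 20%. A stated chance above 55% is therefore suspect on its face.

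These are the only operating characteristics the protocol gives for its holding rules, in the first moderate and severe COPD patients to receive the vaccine. The iSRC applies rule 2 at its safety evaluations, and under section 9.10.2 those evaluations gate Dose 1 in GOLD 3 subjects and Dose 2 in each GOLD grade. A reader is told that a 20% rate of severe reactions would trip the rule more often than not. If the figure is wrong, the error is in the reassuring direction.

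**Working it through.** **Inputs.** The threshold comes from Table 24: at least 25% and at least 2 subjects. Group sizes (10 and 20) and the true rates (20% and 1%) come from the text and the Figure 3 caption.

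**Method.** For n vaccinees the smallest triggering count is r = max(2, 0.25n rounded up). The chance of meeting the rule is the exact binomial tail P(X ≥ r | n, p). For n = 10, 0.25 × 10 = 2.5, so r = 3. For n = 20, 0.25 × 20 = 5 exactly, so no rounding question arises and r = 5. Rule 1 uses r = 1.

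**The plan's other figures, by the same method.**

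| Rule, n | Quantity | Computed | Stated |
|---|---|---|---|
| Rule 1, 10 | not met at 1%: 0.99^10 | 0.904 | >90% |
| Rule 1, 20 | not met at 1%: 0.99^20 | 0.818 | >80% |
| Rule 1, 20 | met at 20%: 1 − 0.8^20 | 0.988 | >98% |
| Rule 2, 10 | met at 20%: P(X ≥ 3) | 0.322 | >30% |
| Rule 2, 10 and 20 | not met at 1% | >0.999 | almost 100% |
| Rule 1, 10 | met at 20%: 1 − 0.8^10 | 0.893 | >90% |

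All reproduce except the last, which falls 0.7 points short; 90% needs a true rate of 20.6%.

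**Rule 2 with 20 subjects.** At p = 0.20:

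- P(0) = 0.0115, P(1) = 0.0576, P(2) = 0.1369, P(3) = 0.2054, P(4) = 0.2182.
- Sum for 0 to 4 events = 0.6296.
- P(X ≥ 5) = 1 − 0.6296 = **0.370**, against a stated figure above 0.55. The gap is at least 0.55 − 0.37 = 0.18.
- P(X ≥ 4) = 0.370 + 0.218 = 0.589. This fits the sentence, but 4/20 = 20% does not meet the 25% threshold.

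**Rates strictly above 20%.** P(X ≥ 5 | 20, p) is 0.414 at 21%, 0.458 at 22%, 0.501 at 23%, 0.544 at 24% and 0.585 at 25%. It reaches 0.55 at 24.1%, so the sentence is false between 20% and 24.1%.

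**Other readings tried, at p = 0.20.**

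- Poisson with r = 5: 0.371. Normal approximation: 0.288, or 0.390 with continuity correction.
- Strictly more than 25% (r = 6): 0.196.
- Two cumulative looks, at least 3 of 10 then at least 5 of 20: 0.455.
- Any group size from 15 to 40 with the 25% threshold: at most 0.402.
- Two independent evaluations, 1 − (1 − 0.370)² = 0.604, or any of three independent rules, 1 − (1 − 0.370)³ = 0.750. Both exceed 55%, but the text speaks of each rule and the caption says nothing is adjusted for multiplicity. Two evaluations would also give 1 − (1 − 0.322)² = 0.541 for 10 subjects, far from the stated 30%.

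**The two rule 2 statements do not share a threshold.** The 10-subject figure fits r = 3, which requires a percentage threshold above 20% and at most 30%. The 20-subject figure fits r = 4, which requires one above 15% and at most 20%. These ranges do not overlap. At a 20% threshold, 10 subjects would need only 2 events, with probability 0.624.

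**The case against.** The figure itself is not defended; the case on the other side is about consequence.

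First, 63% is the chance that one rule at one evaluation with 20 vaccinees is not met. There are three rule 2 criteria and several planned evaluations, and the iSRC sees all available safety data unblinded and can escalate a signal without a numerical trigger. Four severe reactions in 20 vaccinees would be in front of that committee. This stands: 63% is not the chance that safety oversight as a whole misses the problem.

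Second, the only evaluation with a stated size, Dose 1 in GOLD 2 subjects, has about 10 per group, where the rule 2 figure is right. The 20-subject figure is offered as an illustration. This also stands, but later evaluations will have more data, and the 20-subject figure is the only guide given for them.

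Third, Table 24 is clear, it is what the iSRC applies, and the probability sets no sample size or boundary. That is so if the table is correct. The sentence fits a different count, which leaves open whether 4 or 5 of 20 was meant, and those are different safety rules.

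Fourth, the rule 1 discrepancy is trivial, and the text speaks of rates above 20%. Agreed that it is minor; it is still arithmetically off and can be corrected in the same edit.

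**Conclusion.** The statement is wrong as written. Under Table 24, rule 2 with 20 vaccinees has a 37.0% chance of being met at a 20% true rate, against a stated figure above 55%. The chance of not meeting it is 63%, where the text implies less than 45%.

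This assumes independent subjects, one rule and one evaluation, which is how the text frames its figures and how the neighbouring figures reproduce. A count of 4 of 20 is the likely source of the 55%, but the documents do not confirm it. The image of Figure 3 was not available, so the plotted curve could not be checked; the conflict between the sentence and Table 24 does not depend on it. The error lies in the described sensitivity of a safety trigger. It does not affect the sample size or any planned analysis.

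**What to change.** Have the sponsor and the iSRC state which threshold is intended, because Table 24 and the 55% figure cannot both stand.

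- If Table 24 stands: change the rule 2 figure for 20 subjects to about 37% at a 20% true rate, and the rule 1 figure for 10 subjects to about 89%. Check Figure 3 and redraw the 20-subject rule 2 curve if it was computed with 4 events. Adding that these probabilities are per rule and per evaluation would prevent misreading.
- If 4 of 20 was intended: amend the threshold in Table 24 and recompute the 10-subject figure, since a 20% threshold means 2 of 10 (0.624). This changes a safety rule and needs a protocol amendment.

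If evaluations have already been held, record which count was applied. In the first case the cost is corrected text and possibly a redrawn figure, and the stated sensitivity becomes less favourable.

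### With 20 subjects per group, each holding rule 2 has about a 37% chance of being met at a 20% true incidence, not more than 55%

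*Protocol*

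**What the plan says.** Protocol section 9.10.3 defines two sets of holding rules. Rules 1a to 1c need a single subject. Investigators monitor them continuously, and "Meeting any of these holding rules will trigger a hold of vaccination irrespective of the number of subjects vaccinated". Rules 2a to 2c are assessed by the internal safety review committee (iSRC) at its evaluations, and each has the threshold "≥ 25% AND ≥ 2 subjects/group". They count events in the vaccine arm only; rule 2a, for example, reads "Any Grade 3 solicited local AE lasting 48 hours or more in the investigational group".

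The section then gives operating characteristics, presented as examples from Figure 3. At a true incidence above 20 per cent it states:

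- "With 10 subjects/ group": each rule 1 "has more than 90% chance of being met for a vaccine with a true incidence rate above 20" per cent, and each rule 2 "has more than 30% chance of being met for a vaccine with a true incidence rate above 20" per cent.
- "With 20 subjects/ group": each rule 1 has more than a 98% chance of being met, and each rule 2 "has more than 55% chance of being met for a vaccine with a true incidence rate above 20" per cent.

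It also gives the chance of not meeting each rule at a true incidence below 1%: more than 90% (rule 1, 10 subjects), more than 80% (rule 1, 20 subjects) and almost 100% (rule 2, both sizes). The Figure 3 caption says that the curves are for arms of 10 or 20 subjects and are unadjusted for multiplicity.

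**The concern.** A quarter of 20 is 5. At a 20% true rate the expected count in 20 subjects is 4, so the rule needs a count above its expected value. A chance above 55% of reaching 5 is implausible on its face. The rise from more than 30% with 10 subjects to more than 55% with 20 also looks too steep for a threshold that is a fixed percentage and lies above the true rate.

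The vaccine is being given for the first time to patients with moderate and severe COPD, and the protocol gives that as the reason for having holding rules. A favourable iSRC evaluation is required before GOLD 3 subjects receive Dose 1 and before Dose 2 starts in each GOLD grade. This paragraph is where a reader learns how sensitive the numerical criteria are. If the figure is wrong, the reader believes that a vaccine causing a qualifying Grade 3 event in 20% of recipients fails to trigger a given rule less than 45% of the time, when the true figure is higher.

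**Working it through.** **Inputs** (all from Protocol section 9.10.3)

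- Rule 2 threshold: at least 25% and at least 2 subjects, in the investigational group. The smallest qualifying count is r = ceil(0.25 × n): 3 for n = 10 (2.5 rounded up) and 5 for n = 20. The minimum of 2 subjects does not bind at either size.
- Rule 1 threshold: r = 1.
- Arm sizes n = 10 and n = 20; true incidences p = 1% and p = 20%.
- Each rule is taken on its own, as the text and the figure caption do.

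**Formula.** With X the number of subjects with a qualifying event, X ~ Binomial(n, p) and P(rule met) = P(X ≥ r) = 1 − Σ C(n, k) p^k (1 − p)^(n−k), summed over k = 0 to r − 1.

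**Rule 2, n = 10, p = 0.20, r = 3.** P(0) + P(1) + P(2) = 0.1074 + 0.2684 + 0.3020 = 0.6778, so P(X ≥ 3) = 0.3222. The stated figure of more than 30% reproduces, which confirms the method.

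**Rule 2, n = 20, p = 0.20, r = 5.** P(0) to P(4) = 0.0115 + 0.0576 + 0.1369 + 0.2054 + 0.2182 = 0.6296, so P(X ≥ 5) = 0.3704. The stated figure of more than 55% does not reproduce.

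**Rule 1, p = 0.20.** n = 10: 1 − 0.8^10 = 0.8926. n = 20: 1 − 0.8^20 = 0.9885.

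**Rule 1 not met, p = 0.01.** n = 10: 0.99^10 = 0.9044. n = 20: 0.99^20 = 0.8179.

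| Statement | Stated | Computed | Agrees |
|---|---|---|---|
| Rule 1 not met, 1%, n = 10 | > 90% | 90.4% | yes |
| Rule 1 not met, 1%, n = 20 | > 80% | 81.8% | yes |
| Rule 2 not met, 1%, both n | almost 100% | > 99.9% | yes |
| Rule 1 met, 20%, n = 10 | > 90% | 89.3% | no, by 0.7 points |
| Rule 1 met, 20%, n = 20 | > 98% | 98.8% | yes |
| Rule 2 met, 20%, n = 10 | > 30% | 32.2% | yes |
| Rule 2 met, 20%, n = 20 | > 55% | 37.0% | no, by at least 18 points |

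**Where the rule as written reaches 55%.** With r = 5 and n = 20, P(X ≥ 5) is 37.0% at p = 20%, 54.4% at 24%, 58.5% at 25% and 76.2% at 30%. It equals 55% at p ≈ 24.1%. The claim covers every rate above 20%, so it is false from 20% to about 24.1%. For rule 1 with n = 10, 90% is reached at p ≈ 20.6%.

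**Can another reading give more than 55%?**

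- Threshold of 4 of 20 at p = 20%: 58.9%. This fits, but 4/20 = 20% does not meet Table 24. A threshold of 6 of 20 gives 19.6%.
- Threshold of 5 of 20 at p = 25%: 58.5%. This fits too, but the text says 20%.
- Approximations at 5 of 20 and p = 20%: Poisson 37.1%; normal 28.8%, or 39.0% with continuity correction. None fits.
- Slightly different arm sizes: with the 25% rule applied to any arm of 17 to 24 subjects, the probability at 20% never exceeds 37.0%.
- Any one of three independent rules: 1 − (1 − 0.3704)^3 = 75.0%. The text describes each rule separately, and the same pooling with 10 subjects would give 1 − (1 − 0.3222)^3 = 68.9%, far from the 30% quoted there.

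No single threshold of the form at least t reconciles the two rule 2 figures at 20% incidence. Needing 3 of 10 requires 0.20 < t ≤ 0.30; needing 4 of 20 requires 0.15 < t ≤ 0.20. The ranges do not overlap.

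**The case against.** The arithmetic on rule 2 is not open to dispute, but four points limit what follows from it.

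- **Cause.** Figure 3 is not visible in the copy reviewed. A threshold of 4 of 20 (58.9% at 20%) and a misquoted incidence (58.5% at 25% with the correct threshold) explain the sentence equally well. This stands: the cause is unknown, and the curve may be right even though the sentence is wrong.
- **Consequence.** A true rate of 20% lies below the 25% threshold that the sponsor chose, so not triggering is partly how the rule is set. The iSRC reviews all safety data unblinded, can act on other findings, and can meet ad hoc. The one evaluation with a stated size, the gate for GOLD 3 Dose 1, uses about 10 subjects per group, where the quoted rule 2 figure is right. This stands as a limit on the harm. It does not make the stated probability correct.
- **Rule 1.** A gap of 0.7 points could come from reading a curve. This stands: it is a rounding matter, worth correcting only because the paragraph is being edited anyway.
- **Reach.** No rule, visit, sample size or analysis depends on the 55%. The sample size in section 11.4 rests on the chance of detecting an adverse event among 70 subjects. This also stands.

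**Conclusion.** The stated operating characteristic for holding rule 2 with 20 subjects per group is wrong. Under Table 24 the chance of meeting each rule at a 20% true incidence is 37.0%, against a stated figure above 55%. The chance of not meeting it is therefore 63.0%, where the text implies less than 45%. Doubling the arm from 10 to 20 subjects raises the chance only from 32.2% to 37.0%.

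This assumes independent subjects with a common event rate, exactly 20 in the vaccine arm, one rule at one evaluation, and the 25% threshold read literally. The error lies in the description of the rule; Table 24 is clear. Because the figure describes the sensitivity of a safety rule and is far off, it should be corrected. The rule 1 figure for 10 subjects (89.3% against more than 90%) is a marginal second slip.

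**What to change.** Leave the holding rules as they are and correct the text in section 9.10.3:

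- Rule 2, 20 subjects: state more than a 35% chance of being met above a 20% incidence (37.0% at 20%), or more than 55% above a 25% incidence (58.5% at 25%).
- Rule 1, 10 subjects: state about 89% at 20%.
- Check the 20-subject rule 2 curve in Figure 3 and redraw it if it was computed with 4 of 20.
- Confirm that 5 of 20 is the intended trigger. At exactly 4 of 20, Table 24 gives no hold, whereas the quoted probability may have assumed one.

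The cost is two corrected figures and possibly one curve. Conduct, sample size and analysis do not change. The sensitivity shown for rule 2 becomes less favourable, which is the true position.

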10. SUBJECT COMPLETION AND WITHDRAWAL

10.1. Subject completion

A subject who returns for the concluding visit foreseen in the protocol is considered to have completed the study.

10.2. Subject withdrawal

Withdrawals will not be replaced.

10.2.1. Subject withdrawal from the study

From an analysis perspective, a ‘withdrawal’ from the study refers to any subject who did not come back for the concluding visit foreseen in the protocol. A subject is considered a ‘withdrawal’ from the study when no study procedure has occurred, no follow-up has been performed and no further information has been collected for this subject from the date of withdrawal/ last contact.

Investigators will make an attempt to contact those subjects who do not return for scheduled visits or follow-up.

All data collected until the date of withdrawal/ last contact with the subject will be used for the analysis. If the subject agrees, the investigator should make an attempt to collect safety information until the initially planned date for study conclusion, either by phone, or by inviting the subject to a site visit around Day 450.

Information relative to the withdrawal will be documented in the eCRF. The investigator will document whether the decision to withdraw a subject from the study was made by the subject himself/ herself or by the investigator, as well as which of the following possible reasons was responsible for withdrawal:

- SAE.
- Non-serious AE.
- Protocol violation (specify).
- Consent withdrawal, not due to an AE*.
- Moved from the study area.
- Lost to follow-up.
- Other (specify).

*In case a subject is withdrawn from the study because he/ she has withdrawn consent, the investigator will document the reason for withdrawal of consent, if specified by the subject, in the eCRF.

Subjects who are withdrawn from the study because of (S)AEs must be clearly distinguished from subjects who are withdrawn for other reasons. Investigators will

follow subjects who are withdrawn from the study as result of a (S)AE until resolution of the event (see Section 9.5.1.2).

